Endpoints	
The primary outcome is the proportion of hearts transplanted (the number of hearts transplanted divided by the total number of potential donors).
 
The safety outcome is proportion of hearts transplanted that maintain graft function at 30-days and 1-year.
 
Secondary outcomes will include: 1) time from randomization to weaning off vasopressors: defined as being off all vasoactive agents (except for vasopressin); 2) proportion weaned off vasopressors by 12-hours (same criteria as #1); 3) time achieving hemodynamic stability adequate to order first echocardiograph; 4) left ventricular ejection fraction measured on first donor echocardiography; 5) total number of organs transplanted

Population	We plan on enrolling 800 brain dead organ donors with authorization for donation and research in order to have 752 evaluable subjects who receive the study drug or placebo
Phase	Three
Number of Sites	Est. 14 OPOs, 1 coordinating site for human (recipient) data
Study Duration	18-24 months

Abbreviations

AOPO, Association of Organ Procurement Organizations

BD, brain dead

DSMC, data and safety monitoring committee

LVEF, left ventricular ejection fraction

OPO, organ procurement organization

ODRC, Organ Donation Research Council

OPTN, Organ Procurement and Transplant Network

SRTR, Scientific Registry of Transplant Recipients

T4, thyroxine

TTE, transthoracic echocardiography

UNOS, United Network for Organ Sharing

Administrative information

Title {1}	A Multicenter Randomized Placebo-Controlled Trial of Intravenous Thyroxine for Heart-Eligible Brain Dead Organ Donors
Trial registration {2a and 2b}.	Clinicaltrials.gov NCT04415658. Registered June 4, 2020. https://clinicaltrials.gov/ct2/show/NCT04415658
Protocol version {3}	3.0
Funding {4}	None (internal administrative support provided by Mid-America Transplant)
Author details {5a}	[name], Washington University in St. Louis School of Medicine [name], Mid-America Transplant
Name and contact information for the trial sponsor {5b}	Mid-America Transplant [name]
Role of sponsor {5c}	Mid-America Transplant will not have any role in the design or analysis of the trial data. They will not have any role in the writing of the manuscript or the decision to submit the report for publication.

Introduction

Background and rationale {6a}

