There will be a one-month run-in period at each site where screening logs will be checked by the site and central study coordinators for completeness and accuracy. They will review all cases where donors were not enrolled within 24 hours or if other reasons for ineligibility were provided and provide feedback. The site and study coordinators will have weekly conference calls for the first month (and then monthly thereafter) to discuss issues with adherence. They will also provide feedback to individual OPO personnel if study protocols are violated. The study statistician will perform monthly audits of study data for completeness.

Relevant concomitant care permitted or prohibited during the trial {11d}

All standard OPO donor management practices will be continued throughout the study period until and including organ allocation and recovery. The only intervention prohibited is administration of thyroid hormone to those donors allocated to the placebo group for the first 12 hours after randomization.

Provisions for post-trial care {30}

Data collection on non-human organ donors ends at time of organ procurement or end of donor management (for authorized brain-dead potential donors who do not go on to donate organs).

Outcomes {12}

The primary outcome for this study is the proportion of hearts transplanted (the number of hearts transplanted divided by the total number of potential donors – including those authorized but not recovered).

The primary safety outcome for this study is 30-day graft survival in those receiving hearts from those enrolled in this study. This is defined by patient survival with the originally transplanted heart and no mechanical circulatory support. It will be assessed primarily at 30-days but also at 1-year.

Secondary outcomes will include:

1. Time from randomization to weaning off vasopressors: defined as being off all vasoactive agents, except for vasopressin (≤ 1 U/hr)
2. Proportion weaned off vasopressors by 12-hours (same criteria as #1)
3. Vasopressor-inotrope score at 12-hours (excluding vasopressin ≤ 1 unit/hour)
4. Time achieving hemodynamic stability adequate to order first echocardiography
5. Ejection fraction measured on first donor echocardiography
6. Lungs and total thoracic organs transplanted
7. Total number of organs transplanted

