8. Additional outcomes routinely collected from heart transplant recipients will also be aggregated and analyzed, including need for post-transplant mechanical circulatory support and other measures of primary graft dysfunction

Safety endpoints:

The following adverse events will be prospectively collected on all study donors. All events deemed either related or potentially related to the study drug infusion will be reviewed by the site coordinator. Any serious related events (defined as hemodynamic instability leading to cardiac arrest or donor loss prior to organ recovery) will be forwarded to the DSMC for additional review:

1. Severe hypertension (systolic BP > 200 mm Hg)
2. Tachycardia (HR > 150 and increased more than 20 over baseline)
3. New/worsened tachyarrhythmia (SVT, Atrial fibrillation, Ventricular tachycardia or fibrillation)
4. Cardiac arrest or any donor loss prior to the OR
5. Fever – new, above 102 degrees Celsius
6. New skin rash

Participant timeline {13}

Sample size {14}

The proportion of potential heart donors who were able to provide a heart for transplantation in our pilot studies was between 30-60% (12, 14), a rate concordant with the recent literature (23). Proposed effect sizes of thyroid hormone treatment have ranged as high as an absolute increase of 20% or more in proportion of hearts transplanted in non-randomized studies (24); a large retrospective analysis of UNOS data found that those who received thyroid hormone (57% of 40,124 donors) had more hearts transplanted (7). The increase was from 25.8% without treatment to 35% with thyroid hormone (among all donors, not only those who were strictly heart-eligible, as required in this study). Based on our pilot data and this literature, we propose an absolute treatment effect size of 10% as the threshold for this study. In order to detect an increase in the proportion of hearts transplanted from 35% to 45%, we will need 752 total donors (376 per group), assuming 80% power and a one-sided alpha of 0.025. Because we expect some loss of donors after enrollment (e.g., clinical issues that interrupt adherence to the protocol), we will enroll a total of 800 donors (400 in each study group).

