For our safety analysis in recipients of donor hearts, we have calculated a sample size necessary to demonstrate non-inferiority in graft survival. Based on recent data provided by SRTR, the expected 30-day graft survival after heart transplantation is 96%. We will test for a decrease of no greater than 6% in graft survival (i.e. from 96% to 90%; see *Statistical Methods* for a full explanation of assumptions and testing). With one-sided alpha of 0.025, we would need 336 recipients (168 per group) to have 80% power to exclude such a difference. Therefore, based on our sample size of 800 donors and an expectation that overall at least 40% of donor hearts will be transplanted, we expect a minimum of 320 recipients for this analysis; this sample size will provide a power of 78% for non-inferiority. It is likely that more than 40% of hearts will be transplanted; in fact, we saw in excess of 50% of hearts transplanted in our pilot data. Therefore we expect to have more than the required number of recipients to achieve 80% power. This sample size of recipients would also provide 80% power to demonstrate non-inferiority at the one-year survival endpoint.

Recruitment {15}

There are between 50 and 100 heart-eligible organ donors per year managed at most OPOs (of variable sizes) around the country. Therefore we are recruiting at least 10 OPO sites (est. 50 participants per OPO per year) in order to complete recruitment of adequate donors (n=800) within a 18-month study period.

Assignment of interventions: allocation

Sequence generation {16a}

A random sequence of 1s and 0s will be computer-generated by the central coordinating site in blocks of 30 for each participating OPO site (i.e. stratified by site). A web-accessible randomization sheet will be provided to each site with three such blocks (i.e. randomization key for 90 potential subjects).

Concealment mechanism {16b}

Only once eligibility has been confirmed will the on-site organ procurement coordinator will login to the website with the randomization list and determine (using the next available row) to which group the donor has been assigned. The coordinator will enter the UNOS# of the donor on the randomization form, as well as

the time and date of enrollment in the study before communicating the study assignment to OPO staff. The site study coordinator will review the randomization log to ensure that all eligible donors are being randomized and that sequential randomization rows are utilized.

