level of 0.025. We will also present the effect size with confidence intervals for all outcomes. The analysis will follow an intention-to-treat model. However, we will also perform a secondary per-protocol analysis, including only those receiving at least six hours of study infusion. We will also analyze only those in the placebo group who did not receive open-label T4, for a secondary analysis.

We will analyze the primary safety endpoint of recipient graft survival using a non-inferiority method. Our baseline assumption, based on five-year data (from 2016 to 2020) provided by SRTR, is that 30-day graft survival for hearts will be 96%. We assume this baseline rate for both study groups, as there is no evidence to suggest that graft survival is lower in recipients of hearts from donors administered thyroid hormone. In fact, a recent study suggested treatment was associated with improved graft survival (23). The null hypothesis is that heart graft survival is lower in the T4 treated group by at least a clinically significant margin (set at 6%) compared with that observed in hearts transplanted from the placebo donors. This non-inferiority margin was selected with input of the data and safety monitoring committee (DSMC), including a thoracic transplant surgeon and ethicist. It aligns with that used in other trials assessing graft function after heart transplantation which used similar baseline assumptions (96% graft survival) but allowed more liberal margins (10%) (26). We believe that setting the lower limit of tolerance for this safety analysis at 90% graft survival is most appropriate. We will construct two-sided 95% confidence intervals for the difference in graft survival between the groups, allowing us to test for one-sided non-inferiority at alpha 0.025. This will be performed in the intention-to-treat cohort (i.e. all hearts from enrolled donors, by randomized study group) but we will also evaluate non-inferiority using a per-protocol methodology (i.e. evaluating outcomes in recipients who received hearts from donors who received at least six hours of T4 infusion compared to those who did not).

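### The 80% power claimed for one-year non-inferiority has no stated one-year survival rate or margin behind it, and 320 recipients is the expected count under the planning rates, not a minimum

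*Combined protocol and SAP*

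**What the plan says.** **30 days.** Sample size {14} states that "the expected 30-day graft survival after heart transplantation is 96" percent and tests for a fall of no more than 6 points. It gives 336 recipients (168 per group) for 80% power at one-sided alpha 0.025. Statistical methods {20a} repeats the assumption ("is that 30-day graft survival for hearts will be 96" percent, in both groups) and explains the margin: "We believe that setting the lower limit of tolerance for this safety analysis at 90% graft survival is most appropriate".

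**One year.** The Endpoints row of the Protocol Summary names both time points: "The safety outcome is proportion of hearts transplanted that maintain graft function at 30-days and 1-year". Outcomes {12} ranks them: "It will be assessed primarily at 30-days but also at 1-year". The only statement about one-year power is the sentence in Sample size {14}: "This sample size of recipients would also provide 80% power to demonstrate non-inferiority at the one-year survival endpoint". No one-year survival rate or margin accompanies it there or in {20a}.

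**Recipient count.** From 800 donors and heart use of at least 40%, Sample size {14} concludes: "we expect a minimum of 320 recipients for this analysis; this sample size will provide a power of 78% for non-inferiority". It then says that heart use will probably exceed 40%, citing pilot heart use above 50%. Earlier in the section the primary sample size is set "In order to detect an increase in the proportion of hearts transplanted from 35% to 45" percent, with 400 donors enrolled per group.

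**The concern.** Power for non-inferiority depends on an assumed event rate and a margin. The one-year sentence gives neither, and the section's cross-reference to the statistical methods for a full explanation leads to a paragraph built on 30-day survival. The sentence also does not say whether its sample size means 320, 336 or some larger number. Since the Protocol Summary lists one-year function beside 30-day function as the safety outcome, a reader could take one-year non-inferiority to be powered at 80% and misread an inconclusive one-year result.

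The recipient count raises a related difficulty. Heart use of 40% is exactly the average of the planned 35% and 45%, so it already assumes that T4 has its full effect. Calling the resulting 320 a minimum makes the planned case look like the worst case, although graft safety must also be reported if T4 does not raise heart use.

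**Working it through.** **Method.** Unpooled normal approximation, same true survival p in both groups, one-sided alpha 0.025:

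Power = Φ( m / √[p(1−p)(1/n₁ + 1/n₂)] − 1.96 ), where m is the margin.

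**Step 1: reproduce the 30-day figures** (p = 0.96, m = 0.06, both from {14} and {20a}).

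- Sample size: (1.96 + 0.842)² × 2 × 0.96 × 0.04 / 0.06² ≈ 167.5, so 168 per group, 336 in total. This matches the plan.
- 168 per group: SE = √(0.0768/168) = 0.02138; 0.06/0.02138 − 1.96 = 0.846; power 80.1%.
- 160 per group: SE = √(0.0768/160) = 0.02191; 0.06/0.02191 − 1.96 = 0.779; power 78.2%. This matches the plan's 78%.

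**Step 2: carry the 6-point margin to one year.** The documents give no one-year rate, so the rates below 96% are assumptions, used only to show sensitivity. The 400-recipient column is 800 × 50%, the plan's optimistic heart use.

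| Assumed one-year survival | 320 recipients | 336 recipients | 400 recipients |
|---|---|---|---|
| 96% (no net loss after day 30) | 78.2% | 80.1% | 86.5% |
| 95% | 69.2% | 71.3% | 78.6% |
| 92% | 50.7% | 52.7% | 59.9% |
| 90% | 43.2% | 44.9% | 51.6% |

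With this margin, 336 recipients give 80% only if survival is still 96% at one year, and 320 do not reach 80% even then. With 400 recipients, 80% holds down to about 95.2%.

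**Step 3: what a different margin would do.** The margin giving 80% power is (1.96 + 0.842) × √(2p(1−p)/n). With n = 168 per group it is 6.7 points at 95%, 8.3 at 92% and 9.2 at 90%. So 80% is attainable with a wider margin.

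**Step 4: the recipient count** (35%, 45% and 400 donors per group, from {14}).

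- Expected: 400 × 0.35 + 400 × 0.45 = 140 + 180 = 320.
- SD: √[400 × (0.35 × 0.65 + 0.45 × 0.55)] = √190 = 13.8.
- Exact sum of the two binomials: 49% chance of fewer than 320; 13% chance of 336 or more.
- 30-day power with the implied 140 and 180 recipients: 77.6%.
- Both arms at 35%: 800 × 0.35 = 280 expected. SE = √(0.0768/140) = 0.02342; 0.06/0.02342 − 1.96 = 0.602; power 72.6%.

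**The case against.** The case for leaving the text alone has real content.

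- **One year is subsidiary.** The safety objective is stated at 30 days, Outcomes {12} puts 30 days first, and no sample size, stopping rule or primary conclusion rests on the one-year figure. This stands and limits the weight of the point.
- **More recipients may be available.** The one-year sentence follows directly on the expectation of more recipients than required. At 400, power is 86.5% at 96% survival and 78.6% at 95%. This narrows the gap, but at 92% power is still 60%.
- **The margin might apply to both time points.** The null hypothesis in {20a} does not itself name a time point. Even so, its paragraph starts from 30-day survival, and no one-year rate is supplied.
- **320 follows from the stated premise.** If at least 40% of hearts are used, 320 is the floor. The plan discloses the 78%, and the version 3.0 amendment table already calls 320 the expected number. The 49% applies only if 35% and 45% are the true rates. At the 43% heart use of the first pilot (Background {6a}), 344 would be expected, with 30-day power of 81%, although every donor in that pilot received T3 or T4. What remains is that the section uses 40% as the planned average for efficacy and as a lower bound for safety.
- **Intervals are already planned.** {20a} provides two-sided 95% intervals for the graft-survival difference, so an imprecise one-year result would be visible.

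**Conclusion.** Minor to moderate. The 30-day arithmetic is correct. The one-year 80% cannot be derived from anything the documents state. With the only stated margin and no rise in survival after day 30, it is a ceiling reached at 336 recipients and not reached at 320. The size of any shortfall rests on assumed one-year rates and on equal true survival in both groups. Describing 320 as a minimum does not fit the plan's own rates: it is the expected count if the full T4 effect occurs, and with 35% in both arms 30-day power is about 5 points lower.

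Three stronger readings are tempting but not supported:

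- A reader might infer that the 80% is false. A wider one-year margin could produce it and could be legitimate; it is simply not stated.
- A reader might infer that a wider one-year margin would breach the plan's 90% limit. That limit is 96% minus 6 points, set for 30 days, and it does not bind the one-year comparison.
- A reader might infer that the 30-day safety analysis is mis-sized. Its figures reproduce, and the 78% is disclosed.

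**What to change.** In Sample size {14}:

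1. Delete the one-year power sentence, or restate it with an explicit one-year survival rate, margin, recipient number and resulting power. If it is deleted, report the one-year difference between groups with the two-sided 95% interval already planned in {20a}. With 160 recipients per group the expected half-width, 1.96 × √(2p(1−p)/160), is about 4.8 points at an assumed 95% survival and 6.6 at 90%.
2. Replace the description of 320 as a minimum with wording such as: *about 320 expected under 35%/45% (78% power); about 280 (73% power) if both arms are 35%*.

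The cost is a few words and a slightly less favourable stated power. No donors are added, and the primary test, the 30-day non-inferiority test and its margin stay as they are.

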Primary: Intravenous thyroxine (T4) will increase the proportion of hearts transplanted when given early after brain death to heart-eligible hemodynamically unstable potential organ donors

Safety: Hearts transplanted from donors receiving T4 will have non-inferior graft survival to those from the placebo group at 30-days

Secondary: T4 will reduce time to wean off vasopressors and improve cardiac ejection fraction

Trial design {8}

Randomized in parallel groups to intravenous thyroxine or saline placebo in 1:1 ratio

Randomization will be in blocks, stratified by OPO site, allowing each site to serve as its own control (given heterogeneity in donor management protocols between OPOs)

Administration of study drug or placebo will not be blinded

Methods: Participants, interventions and outcomes

Study setting {9}

This study will be performed under the auspices of various Organ Procurement Organizations (OPOs) across the country (list of active sites available on clinicaltrials.gov). Participants will be patients already declared dead by neurologic criteria (i.e. brain dead) and who have provided authorization (first-person or by living surrogates) for both organ donation and for research. They may be physically located either/both in the hospitals in which they were declared and/or at an independent recovery/donor management facility of the OPO. The donor component has been deemed not to involve human subjects research and participating hospitals and OPOs are therefore not engaged in human subjects' research. The coordinating site (Washington University in St. Louis) will be the research site responsible for collecting recipient outcome data. A waiver of consent has been obtained for de-identified collection of this human recipient data.

Eligibility criteria {10}

Inclusion Criteria:

1. Declared dead by neurologic criteria
2. Provided authorization for organ donation and for research
3. Donor age of 14-55 years (inclusive) and weight \geq 45 kg (100 lbs)
4. On one or more vasopressor and/or inotropes (not including vasopressin)

Exclusion Criteria:

1. Brain death declared $>$ 24 hours prior
2. Known CAD or MI (by history, EKG, or previous cardiac cath)*
3. Significant valvular heart disease (by history of echo)*
4. Prior sternotomy or cardiac surgery*
5. Donor at VA hospital
6. Received intravenous or oral thyroid hormone in the past month
7. Known HIV+ status

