8. Other reason preventing donor from receiving study drug (determined by on-site coordinator)

* sufficient to exclude donor heart from being considered for transplantation

Who will take informed consent? {26a}

Donors are dead and their surrogates have all provided authorization for research. This is verified by organ procurement coordinators who are managing the donor management process. Recipients of organs from those enrolled in this study are human subjects but we have obtained a waiver of consent to collect de-identified graft function/outcome data on those receiving hearts from donors enrolled in this trial.

Additional consent provisions for collection and use of participant data and biological specimens {26b}

All data utilized for analysis will be collected as part of donor care including standard UNOS and SRTR data variables (e.g. demographics). No additional biologic specimens will be collected.

Interventions

Explanation for the choice of comparators {6b}

Intravenous thyroxine (T4) is commonly employed at almost all OPOs around the country as part of standard hormonal resuscitation, either for all donors or only those who are hemodynamically unstable (8). It is recommended (without level I evidence) in several donor management guidelines (22). It is usually given as an infusion with or without an initial bolus (protocols vary). A pilot randomized comparison of thyroid hormone formulations (T3 vs. T4) did not suggest any important benefits of T3 over T4 (12). Treatment with T4 will be compared to no thyroid hormone (during the first twelve hours, open-label T4 may be used after).

Intervention description {11a}

Study infusion (saline or thyroxine) will be commenced as soon as possible after randomization. Serum free T4 and TSH levels will be drawn prior to giving the drug. The T4 will be prepared by mixing 500 μ g of drug in

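### Each site is given a 90-row assignment key, and no stated step hides unused rows from the unblinded coordinators who also determine eligibility

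*Combined protocol and SAP*

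**What the plan says.** Trial design {8} describes the trial as "Randomized in parallel groups to intravenous thyroxine or saline placebo in 1:1 ratio", stratified by OPO, with unblinded administration. Under Sequence generation {16a} the sequence is "computer-generated by the central coordinating site in blocks of 30 for each participating OPO site". The same section continues: "A web-accessible randomization sheet will be provided to each site with three such blocks (i.e. randomization key for 90 potential subjects".

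Under Concealment mechanism {16b}, once eligibility is confirmed, the on-site procurement coordinator is to "login to the website with the randomization list and determine (using the next available row) to which group the donor has been assigned". The coordinator enters the donor's UNOS number and "the time and date of enrollment in the study before communicating the study assignment to OPO staff". Afterwards the site study coordinator is to "review the randomization log to ensure that all eligible donors are being randomized and that sequential randomization rows are utilized".

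Implementation {16c} has the same procurement coordinators determine eligibility, enrol the donor and obtain the allocation. Section 17b says that coordinators are not blinded. Exclusion 8 in Eligibility criteria {10} leaves them some discretion: "Other reason preventing donor from receiving study drug (determined by on-site coordinator".

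No section says that unused rows are masked, locked or released singly.

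**The concern.** In an open-label trial, allocation concealment is the main protection against selection at entry. A coordinator who knows the next arm can let it influence whether a borderline donor is enrolled.

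Staff may well have treatment preferences, since section 6b describes T4 as "commonly employed at almost all OPOs around the country". Holding back unstable donors when saline is next would leave a more stable placebo group and bias the result against T4. Holding back promising donors at the same point would bias it in favour of T4.

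Neither form of selection is repaired later. Intention-to-treat preserves the groups as randomized but cannot correct who was put forward for randomization. The primary chi-square test is unadjusted. The subsequent model in Statistical methods {20a} adds age, blood type and a random site effect, not hemodynamic severity.

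**Working it through.** **1. The list.** 3 blocks × 30 = 90 rows, as stated in 16a. With an estimated 14 OPOs (Protocol Summary) and 800 donors (Sample size {14}), the average is 800/14 ≈ 57 donors per site. One list would therefore cover an average site's whole enrolment.

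**2. What each stated safeguard does.**
- Login only after eligibility is confirmed (16b): limits foreknowledge for a coordinator who has not yet seen the list. It does not hide later rows from one who opened it for an earlier donor.
- Entry of UNOS number, date and time (16b): must come before OPO staff are told. It is not required to come before the coordinator sees the arm.
- Log review (16b), screening-log review in the run-in month and continuing calls (11c), and audit of conduct (23): can detect some selective enrolment afterwards. They do not hide rows.

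**3. Predictability.** With an open list, up to 90 − 1 = 89 later rows are knowable after the first login, if they are noted or shared. With unused rows hidden, and balanced blocks of 30 (m = 15 per arm, following from the 1:1 ratio), the expected number of certain assignments is 2m/(m+1) = 30/16 = 1.875 of 30, or 6.25%. A simulation of 100,000 blocks gave 1.876, and a best guess from past assignments was right about 59.9% of the time. The large block protects well, but only if rows are hidden.

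**4. The plan's own sample size.** For 35% vs 45%, one-sided alpha 0.025, pooled SE under the null and unpooled under the alternative:
- 376 per arm: (0.10 − 1.96 × 0.03573)/0.03554 = 0.843, power 80.0%. This reproduces the plan's 752.
- 400 per arm: (0.10 − 1.96 × 0.03464)/0.03446 = 0.932, power 82.4%.

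**5. Generic sensitivity to a spurious shift d, at 400 per arm.** With 35% in both arms, SE = √(2 × 0.35 × 0.65/400) = 0.03373, and type I error = 1 − Φ(1.96 − d/SE).

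| Net shift | Type I error | Power, 35% vs 45% |
|---|---|---|
| 0 | 2.5% | 82.4% |
| +0.5 points | 3.5% | – |
| +1.06 points | 5.0% | – |
| −0.32 points | – | 80.0% |
| −1 point | 1.2% | 74.1% |

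The 5% row comes from (1.960 − 1.645) × 0.03373 = 0.0106. Any bias of size d gives these figures, whatever its source.

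**6. How much steering that would take.** A 1.06-point shift is 400 × 0.0106 = 4.24 hearts. If the donors left out differ from the average in their chance of giving a heart by an assumed 15, 30 or 65 points (65 being the most possible above 35%), the net number left out is 4.24/0.15 ≈ 28, 4.24/0.30 ≈ 14 or 4.24/0.65 ≈ 7. For −0.32 points (1.28 hearts), the numbers at 15 and 30 points are about 9 and 4.

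**7. Time left at version 3.0.** From 01 December 2020 to 01 November 2021 is 335 days. The 18-month recruitment window (Recruitment {15}) runs 547 days to 01 June 2022, leaving 212 (39%). Anticipated study completion is at 760 days, leaving 425 (56%).

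**The case against.** The strongest reply is that the text does not establish exposure. A website with a login and a next available row fits a gated page as well as an open list, and a check on row order can accompany either. The order of steps is not fixed: 16b requires registration before staff are told, and says nothing on whether it comes before or after the coordinator sees the arm. A reader might infer that the arm is always read before registration, or that coordinators can browse all 90 rows. The documents support neither inference, and this part of the reply stands.

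Opportunity is also limited. At about 50 enrolments per OPO per year, roughly one a week, and with donors excluded beyond 24 hours from brain death, swapping the order of two donors would seldom be possible. Steering would mostly mean leaving eligible donors out, which the log review targets. Most eligibility criteria are objective, and exclusion 8 covers only reasons preventing receipt of study drug. Placebo donors may receive open-label T4 after 12 hours, which weakens any motive to keep them from saline. As step 6 shows, a material shift would take several omissions, net in one direction across sites.

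These points lower the likelihood and probable size of bias. They do not supply the missing step. Reviews detect rather than prevent, and the rule on login protects only until the list has been opened once.

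**Conclusion.** The plan as written does not secure allocation concealment. It gives sites a 90-row key, has the unblinded person who determines eligibility read from it, and checks row order only by later log review. That is an unstated safeguard in an open-label trial, not demonstrated exposure and not evidence that enrolment has been steered.

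If unused rows are masked, bias from viewing later rows is zero. If they are visible, bias could run in either direction and its size cannot be derived from the documents. The +1.06 and −0.32 point figures show how small a net shift would matter at the assumed 35% rate and 400 per arm. They are not estimates of what this mechanism produces. The point is worth fixing because the remedy is cheap and the analysis cannot repair the problem afterwards.

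**What to change.** For remaining enrolments, replace the site-held list with release of one assignment at a time. Show it only after eligibility and the UNOS number have been saved, locked and time-stamped, and keep unused rows inaccessible to site staff. The secure REDCap database described in Data management {19} could serve, if it supports this; the documents do not say. If the website already works this way, state it in 16b and nothing else is needed.

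Block size, sample size and the primary test stay as they are. The cost is one-time set-up and site retraining; the effort is an assumption, since the available system is not described. The change does not protect donors already enrolled. At version 3.0 it could cover the remaining 39% of the planned recruitment window, or 56% of the time to anticipated completion if recruitment ran that long. Enrolment pace is not given.

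Optionally, where time-stamped screening logs exist, compare the share of eligible donors enrolled and the use of exclusion 8 by the arm of the next unused row, and report this as supportive. The documents do not say whether such logs continue after the run-in, and the power of the comparison has not been assessed.
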